7.4 Data and Safety Monitoring Plan

The Principal Investigator will provide continuous monitoring of patient safety in this trial with periodic reporting to the Data Safety Monitoring Committee (DSMC).

Meetings/teleconferences will be held at a frequency dependent on study accrual, and in consultation with the study Biostatistician. These meetings will include the investigators as well as study coordinators, clinical research associates, regulatory associates, data managers, biostatisticians, and any other relevant personnel the principal investigators may deem appropriate. At these meetings, the research team will discuss all issues relevant to study progress, including enrollment, safety, regulatory, data collection, etc.

The team will produce summaries or minutes of these meetings. These summaries will be available for inspection when requested by any of the regulatory bodies charged with the safety of human subjects and the integrity of data including, but not limited to, the oversight of the Office of Human Research Ethics (OHRE) Biomedical IRB, the Oncology Protocol Review Committee (PRC) or the North Carolina TraCS Institute Data and Safety Monitoring Board (DSMB).

The UNC LCCC Data and Safety Monitoring Committee (DSMC) will review the study on a regular (quarterly to annually) basis, with the frequency of review based on risk and complexity as determined by the UNC Protocol Review Committee. The UNC PI will be responsible for submitting the following information for review: 1) safety and accrual data including the number of

patients treated; 2) significant developments reported in the literature that may affect the safety of participants or the ethics of the study; 3) preliminary response data; and 4) summaries of team meetings that have occurred since the last report. Findings of the DSMC review will be disseminated by memo to the UNC PI, PRC, and the UNC IRB and DSMB.

8.0 STATISTICAL CONSIDERATIONS

8.1 Sample Size and Data Analysis Plans

Our sample size justification is based on the primary objective to identify kinases which are differentially expressed between pre (just prior to treatment initiation) and post treatment (patients who developed resistance) after treatment with BRAF+MEK inhibition in melanoma patients.

The kinases will be profiled using Multiplexed Inhibitor Beads (MIBs) coupled with mass spectrometry. We anticipate this technique to capture between 50 – 100 kinases in melanoma patients. The kinase activity is reported as a quant ratio between the experimental and control samples. The Paragon algorithm[10] automatically identifies high confidence peptides that will contribute to the average quant ratio of a kinase. Our sample size justification is based on our ability to detect a meaningful difference in the kinase activity between pre and post treatment. The inherent matching of tumor by patient source pre and post treatment will provide a potential source of positive correlation that may be exploited to improve statistical power (e.g., using a paired t-test). However, in order to be conservative, we compute our statistical power using a two-tailed independent Mann-Whitney test in which the kinase activity is compared in the two groups. Based on preliminary data, we assume that 100 kinases are captured, of which 10% of them are truly differentially expressed between pre and post treatment and a common standard deviation of 0.95 (in \log_2 scale).

Table 1 summarizes the power to detect a true difference of D with a sample size of 20 tumors in each group (pre and post treatment) at FDR of 0.05 to account for multiple testings. For example, we achieve a power of 0.92 to detect a \log_2 difference of 1.32 (or a fold change of 2.5) for each kinase between pre and post treatment.

D=Difference in \log_2 scale	1.00	1.32	1.58	1.81
Fold change (2^D)	2	2.5	3	3.5
Power	0.59	0.92	0.99	1.00

Data Analysis Plans

Exploratory tools such as heatmaps and two-way unsupervised hierarchical clustering will be utilized as visual representation of overall kinome activity. The

univariate analysis of kinase expression will be carried out to identify differentially expressed kinases after FDR adjustment. Since multiple kinases work in concert to regulate their functions, prediction analysis of microarrays (PAM) based on nearest shrunken centroid [9] will also be carried out to identify a subset of kinases that predicts resistance to BRAF+MEK inhibition. We also plan to utilize the kinome pathway as prior information in the analysis for identifying functionally related kinase sets to improve statistical power. Focusing on kinase sets may yield more reproducible and interpretable results.

Fisher's exact test will be carried out to test for association between the mutations at baseline to mutations upon the development of resistance to BRAF + MEK inhibition in each oncogene/tumor suppressor gene. Tumor samples from patients who progress while on study and those who are removed from study and who later progress on the combination treatment will be analyzed as one data set. The p-values will be adjusted via FDR to account for multiple comparisons.

The response rate will be estimated and 95% confidence interval will be computed. Progression-free survival will be evaluated using the Kaplan-Meier method. All demographic and analytic data will be summarized by descriptive statistics. Categorical data will be summarized using frequency tables whereas summary statistics such as means, medians, standard deviation and range will be provided for continuous data.

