2.0 STUDY OBJECTIVES

2.1 Primary Objective

To identify kinases that are differentially expressed pre- and post-treatment with BRAF (dabrafenib) and MEK (trametinib) inhibitors, and to determine a kinome signature predictive of resistance to BRAF/MEK inhibition in stage III/IV melanoma

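### PAM delivers the kinome-signature half of the primary objective with no null reference, error rate or performance criterion, and no handling of the pre/post pairs

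*Combined protocol and SAP*

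**What the plan says.** The second half of the primary objective (Section 2.1) is "to determine a kinome signature predictive of resistance to BRAF/MEK inhibition in stage III/IV melanoma". Section 2.3.1 makes the kinome signature, from pre- and post-treatment biopsies, the primary endpoint.

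In Section 8.1, under Data Analysis Plans, the one step described for finding a predictive subset is PAM, which "will also be carried out to identify a subset of kinases that predicts resistance to BRAF+MEK inhibition". No shrinkage threshold or rule for choosing one is given, and no cross-validation, permutation test, hold-out sample, accuracy target or handling of pairs. The bracketed citation does not supply a procedure: item 9 in Section 10.0 is a clinical abstract on BRAF inhibitor treatment beyond progression.

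The neighbouring analyses do have error control. The plan describes a "univariate analysis of kinase expression will be carried out to identify differentially expressed kinases after FDR adjustment", and for the Fisher tests of mutations: "The p-values will be adjusted via FDR to account for multiple comparisons". Neither adjustment reaches PAM, which yields no p-values. On pairing, the sample-size text says: "The inherent matching of tumor by patient source pre and post treatment will provide a potential source of positive correlation".

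**The concern.** PAM is a selection procedure: it picks a shrinkage threshold and lists whatever kinases survive. A non-empty list is therefore not in itself evidence that pre and post tumors differ. If the threshold is chosen by lowest CV error, that minimum is optimistic because it was used to make the choice.

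Pairing adds a second difficulty. Under Section 6.9 a patient informs the primary objective only with sufficient tissue both before treatment and at progression, so the samples come in pairs. If samples are assigned to folds singly, the partner of a held-out sample usually sits in the training set under the opposite label and pulls the wrong centroid towards the held-out sample. The usual 50% benchmark for CV error then does not apply.

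At stake is whether a reported signature can be told apart from one that chance would produce. This is separate from any confounding of the pre/post contrast by drug exposure, because it arises even when nothing differs.

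**Working it through.** **Inputs from Section 8.1.** The plan assumes analysis "with a sample size of 20 tumors in each group (pre and post treatment) at FDR of 0.05", and "we assume that 100 kinases are captured, of which 10% of them are truly differentially expressed". The SD is 0.95 on the log2 scale, and 50 to 100 kinases are expected.

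**Assumed, because the plan is silent.** Normal data; within-patient correlation 0 to 0.7; between-kinase correlation 0 to 0.5; 30 thresholds; 10-fold CV; the rule that picks the threshold.

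**1. The plan's own figure.** Table 1 gives power 0.59, 0.92, 0.99 and 1.00. With 90 null kinases, 10 true ones and FDR 0.05, the per-test level is

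α* = (10 × power × 0.05) / (90 × 0.95) = 0.5 × power / 85.5.

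At power 0.917 this is 0.4585 / 85.5 = 0.0054. Solved iteratively for a two-sided independent t-test with 20 per group, power is 0.585, 0.917, 0.987 and 0.998, which matches all four cells to rounding. The Mann-Whitney test that the text names gives about 0.51, 0.885, 0.98 and 0.998; that mismatch is a side matter. For this point, what counts is that Table 1 concerns detection of single kinases and contains nothing about PAM.

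**2. What PAM does.** For each kinase and class, d is the distance of the class mean from the overall mean, standardised by the pooled SD plus the median of those SDs. It is shrunk to d′ = sign(d) × max(|d| − Δ, 0). A kinase is listed if d′ is not zero at the chosen Δ. With 40 samples, CV error moves in steps of 1/40 = 0.025, and the minimum is taken over 30 values of Δ.

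**3. Simulation with no pre/post difference.** There were 2 kinase counts (50, 100) × 2 fold schemes (by sample, by patient) × 5 within-patient correlations × 3 between-kinase correlations = 60 scenarios of 400 trials each. The simulation SE is at most √(0.5 × 0.5 / 400) = 2.5 points. Share of trials with a non-empty list:

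| Rule | Range | Median | Scenarios at 60% or more |
|---|---|---|---|
| Minimum CV error, ties to the sparsest model | 32-97% | 94% | 55 of 60 |
| Same, and CV error below 50% | 5-86% | 69% | 36 of 60 |
| One-standard-error rule | 4-81% | 59% | 29 of 60 |

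With folds by patient, the first row becomes 92-97% and the second 67-86%. Under the same null, the FDR-adjusted univariate analysis flags any kinase in about 3% of trials.

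**4. Dependence on correlation.** Separate runs with 100 kinases and folds by single sample gave:

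| Within-patient correlation | 0 | 0.3 | 0.5 | 0.7 |
|---|---|---|---|---|
| Any non-empty list | 91% | 78% | 62% | 42% |
| Non-empty and CV error below 50% | 79% | 40% | 17% | 3% |

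Keeping pairs in one fold gave a non-empty list in 94% and 90% of trials at correlation 0.3 and 0.5. A further set of runs gave 28-97% for any list and 4-86% with CV error below 50%. Taken together, the ranges are roughly 30-97% and 3-86%.

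**5. The chance level when pairs are split.** At correlation 0.5 with folds by single sample, the unshrunken model's null CV error is about 0.83, not 0.50.

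**The case against.** Four points can be made for the plan as it stands.

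*The rates come from rules the plan does not state.* This stands. A reader might infer that the planned analysis would yield a false signature in some fixed majority of trials, say 60-95%. The documents do not support that: they name no threshold rule, fold scheme or correlation, and the simulated rate runs from about 3% to 97% across ordinary choices. What survives is that the error rate is uncontrolled and unknown.

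*The CV error itself is informative.* This also stands in part. A reader might infer that a reported signature would mean almost nothing. But with no difference and correlation 0, CV error of 0.25 or less occurred in about 7-8% of trials, and at correlation 0.5 in 0-2%. With 10 of 100 kinases shifted by 1.00 log2, mean CV error was 0.05-0.07. A reader shown the CV error could often tell signal from noise. Less extreme values mislead: at correlation 0 the mean minimum null error was 0.395, and it was 0.40 or less in 56% of null trials. The plan does not commit to reporting any CV error.

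*PAM does not stand alone.* Section 8.1 bases the sample size on the differentially expressed kinases, runs PAM in addition, and also plans pathway-based kinase sets. Sections 1.1 and 1.7 describe an exploratory aim. Nothing says that a PAM list alone meets the objective, and a null list would normally appear beside a univariate analysis with no findings. This limits the harm. Even so, the signature is part of the primary objective and is the primary endpoint, and prediction of resistance is attributed to PAM.

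*A complete absence of difference is unlikely.* The plan assumes that 10% of kinases differ, and Section 4.2 asks for progression biopsies while on drug. False members of the list may then be the likelier problem. With 10 of 100 kinases shifted by 1.00 log2 and folds by patient, 31-40% of selected kinases were false on average. A test of the overall null does not address this, and the fix must say so.

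**Conclusion.** The point holds as a gap in the method. The FDR control in Section 8.1 stops short of the step that delivers the signature half of the primary objective, and the plan supplies no null reference, performance criterion or pairing rule in its place.

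Respecting the pairing in the folds is not a cure by itself, because it gives the highest rates of spurious lists; a null reference is also needed. All the simulated rates rest on normal data and on the assumed threshold rules, fold schemes and correlations, so they should be quoted as ranges. The univariate half of the primary objective is unaffected. The change should be made before analysis, but it does not call the trial's design into question.

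**What to change.** In Section 8.1, after the sentence on PAM, specify that:

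- cross-validation folds are formed by patient, so that both samples of a pair are held out together;
- the statistic is the minimum CV error over the threshold path;
- its null distribution comes from swapping pre/post labels at random within patients, at least 1,000 times, and repeating the whole procedure each time, including threshold selection;
- a signature is reported as identified only if the permutation p-value is 0.05 or less, and otherwise the kinases are listed as descriptive;
- the CV error is reported with the result;
- the test addresses only whether any pre/post signature exists and does not control false members of the list, so support for individual kinases rests on the FDR-adjusted univariate analysis.

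A reduced form of this rule (59 swaps, 15 thresholds) was simulated. With no difference it declared a signature in 1.0% of trials at correlation 0.5 and 3.3% at correlation 0 (300 trials each). With 10 of 100 kinases shifted by 1.00 log2, the smallest difference in Table 1, it did so in 100% of trials at both correlations; with a 0.6 log2 shift and correlation 0.5, in 87% (100 trials each, SE about 3.4 points). The 1,000-swap version was not simulated.

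The cost is protocol wording and a little more computing, with no new patients or tissue. The downside is that the trial may have to report that no signature was identified.

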1.6.1 Kinomining™

[name] and colleagues have developed a chemical proteomics approach to define the activity of a significant percentage (60%) of the expressed kinome in cells and tumors.[7] The technique involves the use of pan kinase inhibitors immobilized on beads to capture a large percentage of expressed kinases in cells and tumors. The activation state of more than 60% of the expressed kinome, defined by RNA-seq, can be analyzed using mass spectrometry analysis of the captured kinases.

This technique has been used to study, and then rationally design a kinase inhibitor combination therapy for triple negative breast cancer (TNBC). Analysis of a patient TNBC tissue sample showed activated RAF-MEK1/2-ERK1/2 signaling, supporting MEK as a target in TNBC. In TNBC cells and tumors of a genetically engineered C3Tag mouse model (GEMM) of TNBC, MEK inhibition with the MEK inhibitor AZD6244 led to rapid reprogramming of the expression and activity of a group of Tyr and Ser/Thr kinases. This reprogramming bypassed the original MEK-ERK inhibition and demonstrated the resilient nature of the kinome. Mechanistically, we showed that acute MEK inhibitor treatment caused MEK-ERK activity loss resulting in rapid c-Myc degradation, inducing the expression of multiple receptor tyrosine kinases (RTKs) and ERK reactivation. RNAi knockdown of c-Myc induced RTK expression similarly to MEK

inhibition. Based on these results, we predicted and tested a novel small molecule combination therapy of MEK inhibitor and sorafenib for TNBC. The combination synergistically caused apoptosis and tumor regression in the C3Tag GEMM of basal-like/claudin-low TNBC, whereas the single agents of MEK inhibitor or sorafenib were largely ineffective. [7]

The research described above, along with siRNA screens of the kinome in cell lines, is identifying previously untargeted kinases essential for tumor growth and survival. Our belief is that the approach can be extended to human tumors.

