2.3 Primary Endpoint

2.3.1 Kinome signature pathway will be based on comparison of kinome expression from pre- and post-treatment biopsies using Multiplexed Inhibitor Beads (MIBs) coupled with mass spectrometry

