3.2 Main Study Exclusion Criteria

Any subject meeting any of the following exclusion criteria at baseline will be ineligible for study participation:

- 3.2.1** Patients with a history of a prior malignancy are excluded unless they have been disease free for 3 or more years or unless they have a completely resected non-melanoma skin cancer, and/or subjects with indolent second malignancies.

- 3.2.2** History of malignancy with confirmed activating RAS mutation at any time. *Note:* Prospective RAS testing is not required. However, if the results of previous RAS testing are known, they must be used in assessing eligibility
- 3.2.3** Prior treatment with a BRAF inhibitor (including but not limited to dabrafenib (GSK2118436), vemurafenib, and LX281/BMS-908662) or a MEK inhibitor (including but not limited to trametinib (GSK1120212), AZD6244, and RDEA119); **NOTE:** There is no limit to the number of other prior therapies, and patients may be previously untreated.
- 3.2.4** Have a known immediate or delayed hypersensitivity reaction or idiosyncrasy to drugs chemically related to study drug, or excipients or to dimethyl sulfoxide (DMSO).
- 3.2.5** Active GI or intracranial hemorrhage
- 3.2.6** History or evidence of cardiovascular risk including any of the following:
- QTc \geq 480 msec;
 - History or evidence of current clinically significant uncontrolled arrhythmias;
 - Exception: Subjects with controlled atrial fibrillation for >30 days prior to D1 of study treatment are eligible.
 - History of acute coronary syndromes (including myocardial infarction and unstable angina), coronary angioplasty, or stenting within 6 months prior to study entry;
 - Patients with history of hypertension **MUST** have hypertension adequately controlled (BP < 140/90) with appropriate anti-hypertensive therapy or diet **prior to study entry**
- Note:** To be eligible a subject must have an average of BP below < 140/90 based on 3 separate measures. If the subject has a record of BP recordings taken at home and in their medical record, \leq 20% of BPs taken should have numbers > 140/90.
- Patients with intra-cardiac defibrillators or permanent pacemakers;
 - Known cardiac metastases;
 - Abnormal cardiac valve morphology (\geq grade 2) documented by echocardiogram (subjects with grade 1 abnormalities [i.e., mild regurgitation/stenosis] can be entered on study). Subjects with moderate valvular thickening should not be entered on study.

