4.0 TREATMENT PLAN

4.1 Schema

^aPatient must have tumor accessible to biopsy to be eligible if frozen tissue from diagnostic specimen is not available.

^bPatient may remain on treatment after progression if evidence of continuing clinical benefit

^cClinical or radiological

^dReasons may include, but are not limited to, inability to tolerate the combination of dabrafenib and trametinib, receiving other therapy, or completion of 3-years of study treatment without progression

^eThe subject may be placed back on the combination trametinib/dabrafenib therapy as part of his/her standard of care treatment plan

^fThe subject may have a progression biopsy taken after progression on standard of care treatment if the subject is eligible and consents to this biopsy. Progression can be defined clinically or radiologically.

This is an open label study of patients with unresectable stage III and stage IV melanoma with mutant V 600E/K melanoma and tumor that is accessible to biopsy. Patients can have had any number of prior lines of treatment (and may be previously untreated), but may not have previously received either a BRAF or MEK inhibitor for treatment of their melanoma.

Patients will receive the BRAF inhibitor dabrafenib and MEK inhibitor trametinib orally at the RP2D determined in the Phase I/II study (BRF113220): trametinib 2mg QD and dabrafenib 150 mg BID on a continuous basis. A cycle will be defined as 3 weeks in duration. Cycles will be repeated until disease progression (clinical or radiological). Patients may remain on treatment after progression (at the discretion of the investigator) as long as they are still experiencing clinical benefit. Patients will be requested to remain on study medication until the biopsy at progression is performed.

Patients will have a biopsy at baseline and at progression. Some subjects may be removed from study prior to progression for other reasons that include, but are not limited to, an inability to tolerate the combination of dabrafenib and trametinib, a need to receive other therapy, or completion of 3-years of study treatment without progression. If one of these subjects later receives the combination of dabrafenib and trametinib per his/her standard of care treatment plan, then the subject may re-consented for a biopsy upon progression. These subjects are required to consent to re-enter the study for the purposes of having a progression biopsy.

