4.2 Biopsies

At baseline, if patient does not have frozen tissue available (see section 6.6) fresh tissue must be obtained. If possible, the pre-treatment biopsy should be performed after all other eligibility criteria are confirmed. Enough tissue will be collected for both kinomining and NextGen sequencing if available (see section 6.6). Fresh tissue collection of accessible tumor will be repeated **at progression (clinical or radiological)** whether patient continues treatment post progression or

not. In fact, patients will be requested to remain on study medication until the biopsy at progression is performed. For subjects who are withdrawn from study treatment, but are later placed back on the trametinib/dabrafenib combination therapy, a biopsy may be collected from the former study subject at the time of progression from the standard of care trametinib/dabrafenib therapy. These subjects must be consented and placed back on study to allow for attainment of a biopsy at progression. These subjects will then remain on study for safety monitoring, in relation to the biopsy procedure, for 30 days. Subjects who have an ongoing \geq grade 2 or serious AE (SAE) related to the study procedure at 30 days will continue to be followed until the event is resolved or deemed irreversible by the investigator.

If possible, biopsies at progression should be performed within 7 business days of documented disease progression, and optimally within 4 hours of taking that day's study medication. If treating physician decides to continue treatment because the patient exhibits continued clinical benefit from therapy (and the patient agrees) then the biopsy can be delayed until the investigator deems the biopsy feasible as long as patient safety is not compromised. Post-treatment biopsies will not be required for patients removed for reasons other than disease progression; although, as mentioned above, if these subjects then go on to eventually receive the trametinib/dabrafenib combination in the future, as part of their standard of care, of the subject may be re-consented at the time of disease progression. See section 6.6 and laboratory manual. Please also see the note in section 6.9.3 regarding assessment of biopsied lesions per RECIST v1.1.

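### The PAM step compares pre-treatment with progression tissue, so it can describe the on-treatment progressed state but cannot support the part of objective 2.1 about predicting resistance

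*Combined protocol and SAP*

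**What the plan says.** Section 2.1 gives the primary objective two parts: to find kinases that differ before and after treatment, and "to determine a kinome signature predictive of resistance to BRAF/MEK inhibition in stage III/IV melanoma". Section 2.3 states what the signature rests on: "Kinome signature pathway will be based on comparison of kinome expression from pre- and post-treatment biopsies". Section 8.1 describes the comparison as "between pre (just prior to treatment initiation) and post treatment (patients who developed resistance"), and then assigns PAM to "identify a subset of kinases that predicts resistance to BRAF+MEK inhibition". It names no PAM class labels, outcome variable, validation or accuracy measure.

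The sampling rules are elsewhere:

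- **Time points.** Section 4.1: "Patients will have a biopsy at baseline and at progression". No early on-treatment biopsy is planned. Section 4.2 requires no post-treatment biopsy from patients removed for reasons other than progression.
- **Baseline exposure.** Exclusion 3.2.3 begins "Prior treatment with a BRAF inhibitor (including but not limited to dabrafenib" and extends to MEK inhibitors.
- **Exposure at progression.** Section 4.2: "patients will be requested to remain on study medication until the biopsy at progression is performed", optimally within 4 hours of a dose. Section 6.7 adds that drug need not be held beforehand.
- **Who contributes.** Under section 6.9, a patient informs the primary objective if there is enough tissue both before treatment and at progression.

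The background in section 1.6.1 reports that a MEK inhibitor in triple-negative breast cancer models "led to rapid reprogramming of the expression and activity of a group of Tyr and Ser/Thr kinases".

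**The concern.** A signature that predicts resistance has to relate something measured before resistance to whether or when resistance follows. The planned contrast does not do that. It separates two states of the same patients' tumours, and those states differ in drug exposure as well as in resistance. If section 8.1 is followed as written, kinases that separate the two tissue types could be reported as predicting resistance when the data cannot say so. This concerns the stated primary objective, so it affects what the trial may conclude. Baseline kinome and PFS will both be collected, but no planned analysis relates one to the other.

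**Working it through.** **1. What the two classes contain.** Section 8.1 does not state the PAM classes. Pre versus post is an inference, but it is the only contrast defined in sections 2.3 and 8.1.

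| | Baseline sample | Progression sample |
|---|---|---|
| BRAF/MEK inhibitor exposure | none (3.2.3) | on drug, by request (4.2, 6.7) |
| Resistant | no | yes |
| Patients | those with paired tissue (6.9) | the same patients |

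No cell holds on-drug, non-resistant tissue, so the effects of exposure and resistance cannot be estimated separately. Every patient is in both classes, so the class label carries no information that distinguishes one patient from another.

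**2. The plan's own power figures.** Inputs from section 8.1: 20 tumours per group, SD 0.95 on the log2 scale, 100 kinases of which 10 truly differ, FDR 0.05. The per-test alpha that holds the FDR is

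alpha = (10 × power × 0.05) / (90 × 0.95) = 0.00585 × power,

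solved jointly with power.

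| D | 1.00 | 1.32 | 1.58 | 1.81 |
|---|---|---|---|---|
| Stated | 0.59 | 0.92 | 0.99 | 1.00 |
| Two-sample t | 0.585 | 0.917 | 0.987 | 0.998 |
| Exact Mann-Whitney (simulated) | 0.533 | 0.895 | 0.982 | 0.998 |

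The table reproduces with a t-test. It gives the power of the univariate test for any pre/post difference, whatever its cause. It says nothing about prediction.

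**3. What pre/post PAM learns.** This was checked by simulating a nearest-shrunken-centroid classifier. The settings are assumptions except the 100 kinases, the SD and the 20 per group: 20 pairs, within-patient correlation 0.5, shrinkage threshold 2.0, leave-one-patient-out validation, 400 runs, 10 early and 10 late progressors.

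| Shift in 10 kinases from drug | Shift in 10 other kinases marking early progression | Pre/post accuracy | AUC of baseline score for early progression | Early-progression kinases selected |
|---|---|---|---|---|
| 1.32 | 1.32 | 0.920 | 0.497 | 0.00 of 10 |
| 1.32 | 0 | 0.924 | 0.498 | not applicable |
| 0 | 1.32 | 0.500 | 0.500 | 0.00 of 10 |

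The early-progression marker was given to both samples of a patient, so it cancels in the pre/post contrast. That assumption drives the last column. Accuracy would be the same if the first 10 kinases had shifted because of resistance, which is the confounding in step 1 seen from the other side.

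**4. What a baseline-to-outcome analysis could do.** For a baseline kinase in a Cox model of PFS, per SD and with d events,

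power = Φ(ln(HR) × √d − z).

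With d = 20, √d = 4.472. Two-sided z is 1.960 at alpha 0.05 and 2.920 at alpha 0.0035 (0.00585 × 0.59 = 0.0035).

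- HR 1.5: 0.4055 × 4.472 = 1.813. Power is Φ(−0.147) = 0.44 and Φ(−1.107) = 0.13.
- HR 2: 0.6931 × 4.472 = 3.100. Power is Φ(1.140) = 0.87 and Φ(0.180) = 0.57.
- HR 2 with 14 events: 0.6931 × 3.742 = 2.593. Power is Φ(0.633) = 0.74 and Φ(−0.327) = 0.37.

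The hazard ratios and event counts are assumptions; the documents give none. Twenty events would need every patient to progress or die under observation. Section 4.6 allows therapy to stop at 3 years without progression, and section 4.7 records later tumour assessments only if available.

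**The case against.** The strongest reply is that the wording is being read too strictly. Section 2.3 defines the signature as a pre/post comparison, and sections 1.1 and 1.7 state the aim as exploring how tumours acquire resistance. PAM has prediction in its name, and class prediction of the resistant state is a legitimate use. That reading is possible. It would make the remedy mainly one of wording, but exposure would still be confounded with resistance.

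A second reply is that drug effect and resistance are not rivals in this protocol. Section 1.6.1 reports that reprogramming bypassed the MEK-ERK block, and section 1.7 attributes resistance partly to compensatory kinase responses. This stands. A reader might infer that the pre/post signature is only a drug artefact, and the documents do not support that. The cited evidence is also acute exposure to a different MEK inhibitor in breast cancer models, so it makes exposure effects plausible but does not measure them in progressing melanoma.

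Third, remaining on drug until the biopsy is a request, and the 4-hour window is a preference. A reader might infer that every progression sample is on drug; the plan intends this but does not guarantee it.

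Finally, a baseline analysis of about 20 patients is weak, and in a single-arm trial it cannot separate general prognosis from resistance to this combination. This also stands, and it is why that analysis is only optional.

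**Conclusion.** The planned PAM step does not support the predictive half of objective 2.1. This follows from the design: one baseline and one progression sample per patient, no on-drug non-resistant tissue, and no analysis linking baseline kinome to outcome. It assumes that the PAM classes are pre and progression. If others were intended, the plan does not say so.

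The conclusion concerns what may be claimed, so it has no single numerical size. The 92% accuracy and the AUC of 0.50 illustrate it under assumed settings. A reader might take the 0.92 in Table 1 as the chance of a false resistance finding. It is not: it is the univariate power for any true 2.5-fold pre/post difference. Nor does the design rule out that a selected kinase also happens to be predictive; the planned analysis simply could not show it. The pre/post result remains useful for the first half of the objective and for describing mechanisms.

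**What to change.** In sections 2.1 and 8.1:

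1. State that the PAM classes are pre-treatment and progression samples, with leave-one-patient-out cross-validation so that both samples of a patient are held out together.
2. Describe the output as a kinome signature associated with the on-treatment progressed state, in place of the wording about predicting resistance.
3. State that drug exposure and resistance cannot be separated in this contrast.

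Optional, and labelled exploratory: FDR-adjusted Cox regression of each baseline kinase on PFS, in all patients with a baseline kinome and not only those with paired tissue. Report it as association with PFS, and give its limited power as a range over assumed hazard ratios and event counts.

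The cost is revised wording, a more modest claim and a little extra analysis of data already to be collected. No new biopsy, visit or patient is needed.
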